## Study Protocol

**Study Setting.** This study took place at a multidisciplinary, research-oriented weight management clinic located within a large children's hospital in the Mid-Atlantic during February through August of 2019. This clinic accepts patients with obesity aged 6 months to 21 years. Approximately 100 new patients are seen annually. Approximately 39% of the patients seen are Black or African Americans, 28% are Hispanic American and 20% are White Americans. 65% of the patients have Medicaid and 34% are private or commercially insured. The clinic follows the recommended standard of medical management of overweight and obesity. The clinic team conducts a comprehensive evaluation to assess dietary and activity behavior change needs of each patient and family, as well as obesity-associated comorbidities. In addition to management of comorbidities, goals for improved physical activity and dietary behaviors are set with the patient and family at each visit.

**Inclusion and exclusion.** Adolescents were eligible if they were between the ages of 12 – 17, a current patient of the affiliated obesity clinic, and had a BMI greater than 30 kg/m^2. Adolescents were ineligible if they had a known genetic cause of obesity, had been diagnosed with a severe intellectual or learning disability, had been diagnosed with an autism spectrum disorder or current psychosis, or were currently in psychotherapy. These exclusion criteria were selected because they might influence the degree to which an adolescent responds to behavioral weight loss and/or their ability to actively take part in a standard mindfulness intervention.

**Recruitment.** Medical providers and other clinic staff were informed about the study and referred interested patients' parents/caregivers to the research team. Interested patients were screened for eligibility and eligible patients were consented in the presence of a parent/caregiver and scheduled to complete a baseline assessment.

**Participant assessment schedule and measures.** Participants completed a series of assessments within a private clinic room at the obesity clinic. These measures were completed at baseline and post-intervention, unless otherwise stated.

### ***Feasibility outcomes.***

*Assessing recruitment feasibility.* Recruitment feasibility was examined through research staffs' detailed tracking of recruitment processes (e.g., referrals from physicians, patients approached in the waiting room), the number of interested patients, and the number of patients eligible after the initial screening. We documented all cases of ineligibility and the reason for disqualification.

*Assessing retention feasibility.* Retention feasibility was tracked via attendance; research staff took attendance during each assessment period and intervention session. Any enrolled participants who dropped out (defined as participants who either explicitly stated that they would like to leave the program or who missed two consecutive sessions in a row without contacting the research team) were contacted by phone to inquire about their reasons for ending the program, as a method of assessing any barriers to intervention completion.

*Assessing participant satisfaction.* We assessed participants' satisfaction with the mindfulness intervention by having them complete a satisfaction survey at the end of the intervention. This survey evaluated: 1) reactions to the topics discussed and skills reviewed; 2) comfort with facilitators; 3) opinions of the materials used; and 4) overall satisfaction with the intervention at that point in time. Ten of these items were scored on a Likert-scale of 1 (strongly disagree) to 5 (strongly agree) (e.g., "Participating in this program helped me to better manage my eating habits") and eight of these items invited open-ended responses (e.g., "What were the challenges of participating in this study?"). Participants were also asked to report their favorite and least

favorite components at the end of each session. This feedback will inform potential adaptations made to the intervention prior to a larger randomized controlled trial (RCT).

### **Participant self-report measures.**

*Demographic questionnaire.* Assesses age, gender, and race/ethnicity. This measure was only completed at baseline assessment.

*Mindful Attention Awareness Scale-Adolescent (MAAS-A).* The MAAS-A is a 15-item measure of dispositional mindfulness. Participants rated how frequently they experience episodes of mindless behavior (e.g., “I find myself doing things without paying attention.”) on a scale of 1 (almost always) to 6 (almost never). This measure has established psychometric properties in diverse adolescent samples.

*Eating Disorders Examination-Questionnaire (EDEQ).* Participants reported instances of overeating, loss of control eating, and binge eating over the last four weeks via 3 items of the EDEQ. This measure was selected to examine potential changes from baseline to post-assessment in eating behaviors that are associated with emotion regulation and risk for obesity that might be influenced by mindfulness training. The EDEQ yields reliable and valid scores. Adolescent responses to the EDEQ correspond strongly with clinical interviews assessing disordered eating.

*Difficulties in Emotion Regulation Scale – Short Form (DERS – SF).* The DERS-SF is an 18-item, widely used self-report measure of emotion regulation problems that has been validated in adolescent samples. This measure was selected to examine potential changes from baseline to post-assessment in emotion regulation, which is theorized to be a key driver of disordered eating (e.g., binge eating, overeating) in adolescents with obesity.

*Youth Quality of Life Instrument – Short Form (YQOL-SF).* The 15-item YQOL-SF measures generic quality of life in youth with and without chronic conditions, ages 11-18 years. It has established psychometric properties in adolescent samples.

### **Executive function measure.**

*Go/No-Go Task.* The Go/No-Go Task examines inhibitory control via a computerized program. This measure was selected to examine potential changes from baseline to post-assessment in impulse control, which is associated with binge eating and obesity, to provide evidence of the cognitive mechanisms through which MBIs might improve eating behaviors. Participants are instructed to press a button (or “Go”) when a certain image is shown on the screen (i.e., an image of food). They are instructed not to respond (or “No-Go”) when another image is shown on the screen (i.e., an image of a toy). The entire task is approximately 15 minutes and each image is shown on the screen for approximately 500 milliseconds. Poor impulse control is evident by more failures to inhibit responses in the No-Go condition (e.g., a false alarm). Omission occurs when a participant fails to respond to a Go stimuli. Reaction time is the processing speed for correct Go trials. This task demonstrates reasonable reliability and validity in adolescent samples.

### **Anthropometric and CVD biomarker measures.**

*Anthropometrics.* Height and weight was assessed in order to calculate BMI. Height was measured to the nearest 1/8 inch using a wall-mounted stadiometer. Weight was measured in indoor clothing, without shoes, to the nearest .1 lb using a calibrated digital scale.

*Blood pressure measurement.* Blood pressure was measured using an automatic upper arm cuff while the participant was seated. Participants were instructed to sit quietly, with both feet uncrossed on the floor, and their arm in a still position, to increase accuracy of each measurement.

**Intervention.** The mindfulness intervention consisted of 6 weekly sessions, blending material from the evidence-based Learning to BREATHE and Mindfulness-Based Eating Awareness Training manualized interventions. Participants met individually with a therapist for each 60-minute session. Sessions focused on: experiential mindfulness exercises, such as mindful eating, loving kindness practices, breath awareness, and mindful movement; hunger and satiety awareness; improving responses to emotions; practicing acceptance and being non-judgmental; and tolerating negative feelings and sensations, including those related to hunger and cravings. Participants were assigned brief homework exercises (approximately 10 minutes) daily in between appointments. Sessions were offered via telemedicine to improve attendance.

**Adverse Events and Criteria for Discontinuation.** Expected risks to participants in this study were generally mild. There was the unlikely but possible risk that participants could experience negative emotions during the practice of mindfulness. Participants were informed about this risk during the consent process and encouraged to inform a member of the research team if they had a strong negative reaction. Mindfulness facilitators were trained to provide adaptations to the mindfulness exercises in order to reduce the intensity of these experiences and ground the participant in the present moment. If an individual continued to experience intense negative emotions that interfered with their ability to participate in the program despite these adaptations, they would have been withdrawn from the study and provided with appropriate referrals. The investigators and research staff met regularly to discuss participants' reactions to the assessments and intervention and any study withdrawals. No adverse events were reported.

**Facilitators and Training.** The mindfulness components of the intervention were facilitated by two interventionists with established mindfulness practices, including one graduate-level clinical psychology student and one first-year medical student. Each facilitator received extensive supervision from the first and second authors (both licensed clinical psychologists) via weekly meetings. Participants met with the same facilitator throughout the course of the intervention. The usual care components were facilitated by medical providers within the obesity clinic.

**Adequacy of Sample Size.** Our study's primary aim was to examine feasibility and refine aspects of the research approach; therefore, a formal sample size calculation was not warranted. Given budgetary and logistical constraints, our aim was to recruit 15 adolescents over a six-month period through a single clinic site, which is sufficient to provide useful information about the feasibility of the protocol.

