### **Statistical Analysis Plan**

IBM SPSS Statistics version 24 was used to complete all quantitative data analyses. Frequencies were used to examine feasibility, including recruitment and eligibility rates, rates of attendance at each session and assessment appointment, and satisfaction with the intervention. Paired *t* tests were conducted to examine pre-post differences in the health outcomes of interest and Cohen's *d* effect sizes and confidence intervals were calculated to examine the effect size of any changes in BMI, mindfulness, emotion regulation, eating behaviors, quality of life, impulsivity, and blood pressure. For participants who did not complete post-assessment (*n* = 3), we used a last observation carried forward imputation.

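### BMI change in 12-17 year olds is analysed only as raw BMI with no comparator; add one supplementary age- and sex-referenced BMI result, with the actual interval beside it

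*Combined protocol and SAP*

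**What the plan says.** - **Population.** Under Inclusion and exclusion, "Adolescents were eligible if they were between the ages of" 12 to 17 and "had a BMI greater than 30 kg/m"². This is one fixed threshold for every age and both sexes.
- **Measure.** Under Anthropometrics, "Height and weight was assessed in order to calculate BMI". No z-score, percentile or percent of a reference percentile appears anywhere.
- **Analysis.** The Statistical Analysis Plan uses paired t tests, with Cohen's d and confidence intervals "to examine the effect size of any changes in BMI" and six other domains. There is no between-group contrast. A randomised trial is mentioned only as a later step, and clinic usual care runs alongside the intervention.
- **Timing.** "These measures were completed at baseline and post-intervention, unless otherwise stated". No target week or visit window follows. The intervention has six weekly sessions, and the study took place "during February through August of 2019".
- **Missing data.** Three participants had no post-assessment, and for them "we used a last observation carried forward imputation".
- **Role of BMI.** Adequacy of Sample Size makes feasibility the primary aim, with a recruitment target of 15.

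**The concern.** BMI normally changes with age across 12 to 17 years. A raw pre-post difference in a single group adds that expected change to anything else that happened, and nothing in the plan separates the two. An age- and sex-referenced measure would take out the average change seen in the reference population.

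How much this matters depends on the time between the two measurements, which a reader cannot learn from the documents. The stake is how the BMI effect size and its interval are read. It does not touch the feasibility conclusions, and no decision rule rests on BMI.

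**Working it through.** The plan gives no SD, effect size or power for BMI, so there is no stated figure to reproduce. The question is how large age-related drift could be beside the precision of the planned estimate.

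**Inputs from the documents**
- Recruitment target 15; three without post-assessment. If 15 enrolled, there are 12 observed pairs. Actual enrolment is not stated.
- Six weekly sessions: at least 5 weeks from first to last.
- Study window: 1 February to 31 August 2019 is 211 days, 211/7 = 30.1 weeks. This is a ceiling, not an estimate.

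**Assumed inputs (not in the documents)**
- Age-related BMI change: r = 0.5-1.0 kg/m² per year, upward.
- SD of BMI change: s = 0.5-1.0 kg/m².

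**Drift in completers** = r × weeks/52
- 5 weeks: 0.5 × 5/52 = 0.048 to 1.0 × 5/52 = 0.096 kg/m²
- 6 weeks: 0.5 × 6/52 = 0.058 to 1.0 × 6/52 = 0.115 kg/m²

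**Planned analysis: 15 participants, three carried forward.** Measures were taken only at baseline and post-intervention, so a carried value is the baseline value and the change is zero.
- Mean drift = (12/15) × drift: 0.8 × 0.058 = 0.046 to 0.8 × 0.115 = 0.092 kg/m².
- Expected variance of the 15 changes = 0.8s² + (2.4/14) × drift². With s = 1.0 and drift 0.058 the SD is 0.895; with s = 0.5 and drift 0.115 it is 0.450.
- Half-width of the 95% interval = t(0.975, 14) × SD/√15 = 2.145 × SD/3.873: 0.496 and 0.249 kg/m².
- Drift as a share of the half-width: 0.046/0.496 = 9% to 0.092/0.249 = 37%.
- Drift as Cohen's d, if d uses the SD of change: 0.046/0.895 = 0.05 to 0.092/0.450 = 0.21. If d uses a baseline SD (assumed 5-8 kg/m²), it is 0.046/8 = 0.006 to 0.092/5 = 0.018. The plan does not say which SD is used.

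**Observed pairs only, n = 12**
- Half-width = t(0.975, 11) × s/√12 = 2.201 × s/3.464 = 0.635s.
- Share: 0.058/0.635 = 9% to 0.115/0.318 = 36%.

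**Dependence on the interval.** In 12 pairs, drift equals the half-width at 0.318/1.0 × 52 = 16.5 weeks to 0.635/0.5 × 52 = 66 weeks. At six weeks sampling error dominates throughout the assumed range.

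**Why no carried-forward line for a referenced measure.** Take a carried BMI of 35, and a 95th percentile of 24-30 rising by 0.5-1.0 per year (assumed). Re-scoring at an age six weeks older lowers percent of the 95th percentile from 35/30 = 116.7% to 35/30.058 = 116.4% (0.2 points), up to 35/24 = 145.8% to 35/24.115 = 145.1% (0.7 points). That fall comes only from the imputation. Carrying the standardised score forward avoids it, but then assumes that raw BMI rose with the reference, which contradicts the raw-BMI carry-forward for the same three people.

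**The case against.** The strongest reply is that this hardly matters. Feasibility is primary, BMI is one of seven exploratory domains, and six weekly sessions suggest an interval near six weeks, where the drift is small. The size rests entirely on outside assumptions, and the upper figures pair the fastest rise with the smallest SD. A referenced measure still leaves usual care, regression to the mean and season in the estimate, and it adds another post hoc result to a very small study. All of this stands, and it keeps the point at the level of a cheap improvement.

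It does not remove the point. Referencing is a better method for an uncontrolled change in this age group, it needs no new measurements, and the plan already commits to an effect size and interval for BMI.

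Two stronger readings are tempting. A reader might infer from the seven-month window that intervals were long and drift substantial. The documents do not show this: the 30-week ceiling needs baseline on the first day and post-assessment on the last, and the retention rule counts two consecutive missed sessions without contact as drop-out, which limits slippage. A reader might also infer that growth could produce a false benefit. Under an upward drift it would do the opposite.

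**Conclusion.** The point holds as a low-stakes improvement to the analysis. Raw BMI change with no comparator includes expected age-related change. At about six weeks this is 0.06-0.12 kg/m² in completers, or 9-37% of the half-width under the planned carry-forward. These figures assume a rise of 0.5-1.0 kg/m² per year, an SD of change of 0.5-1.0 kg/m², 15 enrolled, and an interval near six weeks. The direction is upward: a BMI fall could be masked, or a small rise shown. Nothing here makes the planned raw-BMI result invalid or affects the feasibility findings. The unstated interval is a gap in reporting; it is not evidence of a larger bias.

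**What to change.** Keep the raw BMI analysis as planned, and add:

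1. The paired change, Cohen's d and confidence interval for one age- and sex-referenced measure suited to BMI above 30, for example percent of the 95th percentile, labelled supplementary and post hoc.
2. Observed pairs only for that measure, with no carried-forward line. Use age at each visit and sex from the clinic record, because the demographic questionnaire gives age and gender at baseline only.
3. The median and range of the actual baseline-to-post interval, beside that result.
4. A sentence stating that referencing removes only the average age- and sex-related change of the reference population. Usual care, regression to the mean, season and any gain particular to this clinic's patients remain.

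**Cost.** One derived variable, one result line and two sentences. Height and weight were measured at both visits. The plan reports "rates of attendance at each session and assessment appointment", so visit dates are probably on file; these dates, date of birth and sex are assumed to be available. The downside is one extra exploratory result in about 12 observed pairs, if 15 enrolled.

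### No harm-specific question to every participant is described, so a report of no adverse events cannot separate none occurring from none being mentioned

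*Combined protocol and SAP*

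**What the plan says.** The Adverse Events and Criteria for Discontinuation section names one risk: "There was the unlikely but possible risk that participants could experience negative emotions during the practice of mindfulness". Participants heard of it at consent and were "encouraged to inform a member of the research team if they had a strong negative reaction". On the staff side, "Mindfulness facilitators were trained to provide adaptations to the mindfulness exercises in order to reduce the intensity of these experiences", and "The investigators and research staff met regularly to discuss participants' reactions to the assessments and intervention and any study withdrawals". The section ends with a result: "No adverse events were reported".

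Other contacts are described elsewhere. Under Feasibility outcomes, dropouts "were contacted by phone to inquire about their reasons for ending the program, as a method of assessing any barriers to intervention completion". Participants gave their best- and least-liked components after each session and completed an end-of-intervention satisfaction survey, with open-ended items such as "What were the challenges of participating in this study". Facilitators and Training adds weekly supervision by licensed clinical psychologists and one facilitator per participant throughout.

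The Statistical Analysis Plan lists frequencies for recruitment, eligibility, attendance and satisfaction. It lists none for adverse events.

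**The concern.** A count of adverse events means only as much as the way the events were looked for. The one route addressed to participants depends on an adolescent aged 12 to 17 raising the matter unprompted, and then only if the reaction is strong. The named risk is an internal state that an observer may not see. Under-capture of this kind can only push the count towards zero.

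Two things are at stake. A reader cannot tell what the zero means. And the study exists to refine the research approach before a larger randomised trial: if the same way of looking for harm were reused, that trial would under-count the one risk its planners already expect. The protocol's own provisions for adapting exercises and for withdrawal also act only once distress is known.

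**Working it through.** The documents state no adverse event rate or denominator, so there is no figure to reproduce. The check has two parts: what each route can detect, and what a zero can mean at this sample size.

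**1. The described routes side by side**

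| Route | Who it reaches | What it asks or sees |
|---|---|---|
| Invitation given at consent | Everyone | Strong reactions, if volunteered |
| Facilitator in individual 60-minute sessions | Attenders | What shows or is said in the session |
| Staff meetings and weekly supervision | Staff | What has already been seen or disclosed |
| Feedback after each session | Attenders | Most- and least-liked components |
| End-of-intervention survey | Those who complete it | Satisfaction and challenges |
| Dropout call | Dropouts | Reasons for leaving, as barriers |

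No row is a scheduled question about harm asked of every participant. No definition, grading or recording procedure for adverse events is described.

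**2. Time outside sessions**

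Homework is about 10 minutes a day between weekly sessions of 60 minutes. Six days give 6 × 10 = 60 minutes and seven give 70. Home practice is therefore about as long as the session, with no facilitator described as present.

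**3. What zero reports can mean (illustration)**

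Inputs:
- n = 15, the recruitment aim under Adequacy of Sample Size. Actual enrolment is not stated.
- s, the share of affected participants whose event is mentioned or noticed. It is not in the documents; 1, 0.5 and 0.25 are assumed.
- A true rate p of 20% per participant, also assumed.

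Formulas:
- Upper end of the two-sided exact 95% interval for 0/n: 1 − 0.025^(1/n). For n = 15 this is 1 − 0.7820 = 21.8%.
- Limit on the true rate if only a share s surfaces: 21.8% / s.
- Chance of zero reports: (1 − p·s)^n.

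| s (assumed) | Upper limit on true rate | Chance of zero reports if p = 20% |
|---|---|---|
| 1 | 21.8% | 0.80^15 = 3.5% |
| 0.5 | 21.8 / 0.5 = 43.6% | 0.90^15 = 20.6% |
| 0.25 | 21.8 / 0.25 = 87.2% | 0.95^15 = 46.3% |

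The first row is the effect of sample size alone and would be the same under perfect active questioning. Only the change down the table represents incomplete capture, and its size follows entirely from the assumed s. If 12 were the denominator (15 less the 3 without post-assessment), the limit at s = 1 would be 1 − 0.025^(1/12) = 26.5%. Twelve is a doubtful denominator, because those three could have been observed in sessions before they were lost.

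**The case against.** The strongest reply is that participants were watched closely. Sessions were individual and weekly, with the same facilitator throughout and regular supervision by psychologists. The staff meetings covered reactions without any severity threshold. Participants were also asked things: feedback at every session, open-ended items at the end, and a call if they left. Emotion regulation, eating behaviour and quality of life were measured at baseline and post-intervention, and their change was analysed.

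Much of this stands. A reader might infer that nobody monitored for harm, or that participants were asked nothing. The documents contradict both. What does not follow is that these routes amount to asking everyone about harm. The feedback, survey and calls are aimed at acceptability and barriers, and the meetings work from what is already known. The scales give group changes, not events. For the three participants without post-assessment, carrying the last observation forward repeats the baseline value and so enters a change of zero.

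Three further objections also stand. The 21.8% measures small numbers, not passive reporting. The study is described as finished, so new questions cannot be added to it. And the consent pages are not available here and unpublished forms may exist, so the point can only be that no such question is described.

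**Conclusion.** The point holds in limited form. One participant-facing route to report harm is described. It is voluntary and limited to strong reactions, and the other contacts supplement it without any harm-specific question to all. The reported zero is therefore uninterpretable as a rate.

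The size of any under-count is unknown. The 21.8% limit assumes that 15 were enrolled and that every event surfaced; it rises if some did not, by an amount the documents cannot supply. The conclusion rests on the description of the routes and does not need these figures.

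Two stronger readings should be resisted. A reader might infer that the plan claims the intervention is harmless and carries that claim into the larger trial. The text says only that none were reported, and what it carries forward is participant feedback for adapting the intervention. A reader might also take the capture-adjusted limits as evidence of hidden harm. They are consequences of assumed shares, and nothing in the documents shows that any event was missed.

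**What to change.** **This study (reporting only).** State how adverse events were ascertained and recorded, and give the number of participants at risk. If no structured question was used, word the result as no events spontaneously reported or observed. If one was used, describe it. The cost is a few sentences.

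**The protocol as carried into the planned randomised trial.** At each weekly session, at post-assessment and in every dropout call, ask one fixed yes/no question on distress or unwanted effects since the last contact, including during home practice. Record severity and relation to practice, on the same sheet as attendance.

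**The SAP.** Add a line that tabulates participants with any event as n/N, with an exact 95% upper limit.

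The cost is about a minute at contacts that already take place and one line on an existing form. The small downside is that more minor events will be recorded.
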